#### 4.0 Study Endpoints (if applicable)

Primary study endpoints include improvement in cough, measured by dichotomous yes/no response to improvement, the Leicester Cough Questionnaire (LCQ), and a visual analogue scale for symptom severity. Due to its validation, the LCQ will be the primary outcome measure. Secondary study endpoints include the complication and side effect rate from the injections.

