## **10.0 Study Design / Methods**

Figure 2 depicts the flow diagram of the study design. Once patients have met inclusion and exclusion criteria (including undergoing all diagnostic testing for other potential causes of chronic cough) and have agreed to study participation, informed consent will be obtained and they will be randomized into two groups: treatment and placebo. This will be achieved using randomly-assorted, secured envelopes containing a card indicating whether the patient will be in the treatment or placebo group. This will be unveiled immediately to the provider administering the first injection, but remain unknown to the subject. There will be 25 "Treatment" and 25 "Placebo" cards within the 50, individually-secured envelopes. On initial visit, prior to the injection, patients will first undergo nasal laryngoscopy as part of standard of care. If there is any vocal fold weakness seen on scope examination or if there is a unilateral trigger point identified, then the first injection will start on the side of the suspected neuropathy. If there is no evidence of neuropathy on examination, we will start with a left-sided injection. Injections will be standardized to 2 mL of a 1:1 triamcinolone 40mg: 1% lidocaine with 1:200,000 epinephrine. Injection syringe will be brought into room by the physician in an opaque box and placed behind patient so they cannot view the syringe prior to injection. During the injection, a paper "shield" will be held under the patient's chin by an assistant and they will be asked to close their eyes so that they are not able to view the syringe during injection. This is necessary as steroid possesses a white color as compared to clear saline. The practitioner is not blinded so that proper drawing back on the syringe is not compromised to avoid intravascular or airway injection.

[figure not shown]

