### **Figure 2. Flow Diagram of Study Design**

Injection will be completed near the lateral thyrohyoid membrane by a single experienced laryngologist per previously published methodology utilizing bony, soft tissue and cartilaginous landmarks. An illustration of the anatomic target for the injection can be seen in Figure 3. To minimize patient discomfort, lidocaine cream will be applied to the skin prior to injections.

Following injection, patients will be instructed to follow up in a 2- to 3-week time frame; however, we will include all patients in analysis if they follow up within 1-4 weeks. Any follow up outside of that window will lead to removal of the patient's data from the analysis. At follow up, if the patient's cough has improved by greater than or equal to 50% compared to baseline, we will repeat the injection on the same side. If less than 50%, we will move to the other side to perform the injection. Patients will undergo a total of two injections before data collection is complete for analysis. If patients were to experience full resolution of cough (i.e. report 0/10 for cough severity) after the first injection alone, then at that point, their condition would be considered cured and their enrollment in the study will finish. The reason for this is to avoid unnecessary and unindicated injections in patients with resolution of cough.

2 weeks after the second injection, participants will be unblinded. If in the placebo group, they will have the opportunity to complete 2 additional treatment injections (unblinded) under the study protocol. Data will be collected and stored in the same fashion as prior to unblinding.

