## 12.0 Data Management

Descriptional analysis of all demographic data, including sex and age, will be completed. Dichotomous data will be summarized as percentages per group per injection and compared via chi-squared analysis. Changes in Leicester Cough Questionnaire scores, both global and specific domains (physical, psychological and social), will be analyzed via a linear regression model. An independent t-test will then be used to compare both study arms. Regression analysis will also be performed on the data collected from the patient log, specifically the daily visual analogue scale. A ruler will be used to the identify the exact percentage along the scale that represents the patient's cough severity. A comprehensive compilation of side effects reported by the treatment group will be reported as a proportion of the total number of patients in the treatment study arm (n = 25) and compared to the placebo group (n=25). The data collected from the placebo group pre-unblinding will be directly compared to the results achieved from treatment injections offered following unblinding.

Data will not leave MUSC. Patient identifiers (MRN) will be kept coded on a separate, password-protected file stored on a secure drive.

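### The planned comparison of the placebo arm's blinded data with its later open-label injections can show a difference even if the drug does nothing, and should be descriptive only

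*Combined protocol and SAP*

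**What the plan says.** Section 12.0 first sets out the comparison of the randomised arms: chi-squared for dichotomous data, regression for changes in the Leicester Cough Questionnaire (LCQ), then "An independent t-test will then be used to compare both study arms". The paragraph ends with a further comparison: "The data collected from the placebo group pre-unblinding will be directly compared to the results achieved from treatment injections offered following unblinding". For this one the plan gives no test, analysis set, baseline, time point or exploratory label.

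Section 10.0 describes where the second set of data comes from:

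- Timing: "2 weeks after the second injection, participants will be unblinded".
- Entry: "If in the placebo group, they will have the opportunity to complete 2 additional treatment injections (unblinded) under the study protocol". The treatment arm is offered no second pair of injections.
- Earlier exit: for a patient reporting 0/10 after the first injection, "their condition would be considered cured and their enrollment in the study will finish".
- Blinding in the first phase covers the patient only. Of the allocation card the plan says: "This will be unveiled immediately to the provider administering the first injection, but remain unknown to the subject".

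Section 4.0 lists a yes/no answer on improvement, the LCQ and a visual analogue scale, and adds: "Due to its validation, the LCQ will be the primary outcome measure". All three are patient-reported.

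**The concern.** Four things differ between the two sets of data besides the drug. The patient knows in the second phase that the injection is active. Only those who accept the offer contribute, and complete responders to the first saline injection have left by rule. Saline always comes first. No group is followed in parallel to show what time alone would do. A difference between the phases can therefore come from expectation, opt-in, time or the drug, and the data cannot tell these apart.

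This matters here because Section 2.0 names the placebo effect as an open question and Aim 1b sets out to determine it. A before-and-after contrast within the placebo arm could be read as an answer to that question, although it gives up the blinding and randomisation that the trial was built to provide.

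**Working it through.** **The plan's own figure.** Section 12.0 gives no number for this comparison. The only sample-size figure, 18 per group in Section 6.0, belongs to the randomised comparison of 70% with 25%. Reading the stated 80% as power and assuming two-sided alpha 0.05, the arcsine formula gives h = 2·asin(√0.70) − 2·asin(√0.25) = 0.935 and n = 2 × (1.960 + 0.842)² / 0.935² = 17.95, so 18. The figure reproduces and has no bearing on the point below.

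**Step 1: selection alone.** Let B be the score before the first saline injection, S1 the score at the end of the blinded phase and S2 the score at the end of the open-label phase. Higher is better, each has SD 1, and every pair has correlation r. There is no drug, placebo or time effect. Assumed: r from 0.5 to 0.8, and the 75% with the smallest blinded change S1 − B opt in. The 75% is prompted by the 25% placebo improvement in Section 6.0, but the plan states no opt-in rate.

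- The variance of S1 − B is 2(1 − r). A standard normal variable below its 75th percentile has mean −0.3178/0.75 = −0.4237. Opt-in patients therefore have mean blinded change −m, where m = 0.4237 × √(2(1 − r)). This is 0.424 at r = 0.5 and 0.268 at r = 0.8.
- The slope of S2 − S1 on S1 − B is −(1 − r)/(2(1 − r)) = −1/2, so the mean of S2 − S1 in opt-in patients is +m/2.
- The slope of S2 − B on S1 − B is +1/2, so its mean in opt-in patients is −m/2.
- The mean blinded change in the whole placebo arm is 0.

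| Reading of the comparison | Formula | r = 0.5 | r = 0.8 |
|---|---|---|---|
| Opt-in patients, each phase from its own baseline | 1.5m | +0.64 | +0.40 |
| Opt-in patients, both phases from the original baseline | m/2 | +0.21 | +0.13 |
| Opt-in patients from a new baseline, against the whole placebo arm | m/2 | +0.21 | +0.13 |
| Opt-in patients from the original baseline, against the whole placebo arm | −m/2 | −0.21 | −0.13 |
| Everyone opts in, any of the above | 0 | 0 | 0 |

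Values are in SD units; positive favours the open-label injections. The wording of Section 12.0 admits every row.

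**Step 2: expectation or time added.** Simulation of 25 placebo patients (Section 12.0) with a 25% response in the blinded phase (Section 6.0), no drug effect and independent responses in the two phases. The open-label rates are assumed. Entries are the chance of a significant result in the drug's favour; the nominal value is 2.5%.

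| Open-label response | All opt in, McNemar | All opt in, chi-squared | Only non-responders opt in, McNemar |
|---|---|---|---|
| 25% | 1.1% | 2.7% | 32% |
| 35% | 6% | 12% | 68% |
| 45% | 21% | 34% | 90% |
| 55% | 46% | 63% | 98% |

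The last column is high even in its first row because patients chosen for not responding can only stay the same or improve. For a continuous score with 25 patients and a paired t-test, a drift of 0.2, 0.3 or 0.5 SD of the within-patient difference (assumed) gives 16%, 30% and 67%.

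**Step 3: cases that run the other way.** If response is a stable trait and only non-responders opt in, their open-label response is 12% to 20%, below the 25% of the whole arm. If patients enrol when their score is by chance low (error in B shifted down by half its SD, assumed), all opt in, and each phase is measured from its own baseline, the difference is −0.5 × √(1 − r): −0.35 at r = 0.5 and −0.16 at r = 0.9. It is significant against the drug in about 16% of trials.

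**Step 4: what the randomised data offer.** At 25 per arm, 70% against 25%, two-sided 0.05: the SE under the null is √(2 × 0.475 × 0.525/25) = 0.1412, and under the alternative √((0.21 + 0.1875)/25) = 0.1261. Then z = (0.45 − 1.96 × 0.1412)/0.1261 = 1.37, so power is 91.5% with all 25 per arm analysed. This is for the dichotomous outcome; the plan gives no figure for the LCQ.

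**The case against.** The best defence is that this is one closing sentence, placed after the randomised comparison, with no endpoint status or hypothesis attached. It does not replace the comparison of arms. That stands, and it limits the point to how one supplementary comparison is labelled and interpreted.

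A reader might infer more, in three ways that the documents do not support.

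- That the comparison must favour the drug. Step 1 gives zero with full opt-in, and one admissible reading gives a negative value. Quoting only +0.40 to +0.64 SD would pick the most favourable of several definitions.
- That regression to the mean generally helps the active phase. Regression from the enrolment score falls mainly in the first phase, which is saline. Only the regression created by opt-in can favour the open-label phase.
- That an unpaired test is planned on paired data. Section 12.0 names no test for this comparison and ties the independent t-test to the two study arms. If one were used, its standard error would be too large by 1/√(1 − ρ), that is 1.20 to 1.83 times for an assumed within-patient correlation ρ of 0.3 to 0.7. In a comparison with no bias that makes a false positive less likely.

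What survives is that the phases differ in blinding, selection and order, and that the plan leaves open the choices that fix the sign of the bias.

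**Conclusion.** The point holds as a matter of interpretation. The planned comparison is unblinded, self-selected, fixed in order and without a concurrent control, on patient-reported outcomes, so it can show a difference when the drug has no effect. Selection alone spans about +0.64 to −0.21 SD under the assumed 75% opt-in and correlation of 0.5 to 0.8, and is zero if all opt in. Expectation or time effects would be added to that; their size is not known from the documents, and the rates in Step 2 only illustrate it.

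It would be wrong to conclude that the main efficacy test is compromised. The comparison of randomised arms before unblinding does not use these data.

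**What to change.** In Section 12.0, replace the sentence on the direct comparison with text to this effect:

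- Open-label results in placebo patients are reported descriptively, as uncontrolled, paired within-patient results in those who opted in.
- The pre-injection score is the LCQ from the follow-up visit after the second blinded injection, where available. Section 10.0 already collects the LCQ at each follow-up visit, so a further questionnaire may not be needed. Because unblinding is set at two weeks and follow-up visits may fall at one to four weeks, record whether that score was completed before or after disclosure.
- The number who opted in and their blinded-phase response are shown beside the results.
- A note says that selection and expectation can bias the estimate. It is needed even with paired change from the new score: in Step 1 that quantity still carries +0.21 to +0.13 SD from opt-in alone.
- Efficacy conclusions, including any about the placebo effect, rest only on the randomised pre-unblinding comparison.

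The cost is a paragraph of wording. The offer of open-label injections does not change. The sponsor gives up a secondary comparison that might have looked favourable.

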## 13.0 Provisions to Monitor the Data to Ensure the Safety of Subjects (if applicable)

The patients will keep a log of all symptoms and concerns throughout the treatment. This will be helpful in determining the side effect rate from injections, but more importantly, provides a way to monitor patient safety throughout the procedure. At minimum these will be reviewed every 4 weeks, but more likely every 2 weeks. Patient's will also be provided with a direct communication line if they have questions or concerns related to the injection.

If any serious adverse events were to occur, these would be immediately reported to the IRB and the study would terminate out of respect for patient safety. Data reviewed include safety data, untoward events, and efficacy data. The primary investigator will review the data.

Participants may withdrawal from study participation at any point if they choose to do so without any influence or coercion.

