Several treatments have been explored for neurogenic cough, including the use of neuromodulating medications (i.e. amitriptyline, gabapentin, pregabalin, baclofen, and tramadol). Ryan et al. found that about 67% of patients taking amitriptyline for chronic cough had greater than 50% improvement in symptoms; however, 64% of patients discontinued use of the medication at follow up. Of these patients, 48% discontinued amitriptyline due to its side effects, which include sedation, dry mouth, anxiety, insomnia, weight gain, and dizziness. Similarly, gabapentin and pregabalin have shown some efficacy in the treatment of neurogenic cough, but they are not effective in all patients and there are concerns for systemic medication side effects. Dion et al. have proposed further evaluation of tramadol for neurogenic cough, however, opioid dependence is a significant concern. In addition to neuromodulating medications, suppression (cognitive behavioral) therapy can be a useful adjuvant but is more effective when combined with medical therapy. Lastly, botulinum A injections and injection augmentation have been suggested for chronic cough, but have been found to have limited use in clinical practice.

Superior laryngeal nerve (SLN) blocks, which involve a percutaneous injection of lidocaine and steroid, have been widely described in the Anesthesiology literature as a safe and effective anesthetic during awake fiberoptic intubation. The literature on superior laryngeal nerve blocks for the treatment of chronic cough is limited, but there are two published retrospective studies supporting the efficacy of in-office SLN injections Simpson et al. reported a series of 18 patients who underwent an average of 2.4 SLN blocks with a statistically significant decrease in cough severity index scores from 26.8 to 14.6 following treatment. No significant adverse outcomes were reported. Dhillon similarly showed a statistically significant decrease in post-treatment cough severity index scores following SLN injections in a cohort of 10 patients without any adverse effects.

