Recently, we retrospectively reviewed our experience at the Medical University of South Carolina with in-office SLN blocks for the treatment of chronic neurogenic cough and our unpublished data are consistent with the work of Simpson, et al. and Dhillon. We found that within a cohort of 23 patients (4 males, 19 females, average age 63.6 years), 17 (74%) reported improvement with the injections, 2 (9%) reported initial improvement followed by return to baseline, and 4 (17%) did not have any improvement. The average number of SLN blocks performed per patient was 3.8. Of the 23 patients, 13 had recorded pre- and post-treatment Hull Cough Sensitivity Questionnaire scores and changes in scores were significantly improved from an average of 38 to 23 ( $p = 0.005$ ). All patients reported their symptom severity on a scale of 0-10 and there was a significant negative correlation between the number of injections and symptom severity scores with the largest difference following the initial injection (Figure 1). There were no major adverse events, however 4 patients (17%) reported self-limited post-injection globus sensation.

Although the current data support the efficacy and safety of SLN blocks for chronic neurogenic cough, there are no prospective investigations. Questions remain regarding safety and efficacy, particularly the potential for placebo effect, as well as proper medication dosing and timing. Our hypothesis is that superior laryngeal nerve blocks will provide significant improvement in cough severity compared to placebo. By better understanding the efficacy of superior laryngeal nerve blocks in the treatment of chronic cough, the care of patients presenting with this common symptom will be optimized.

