## **6.0 Number of Subjects**

We will recruit 50 patients. Our institution has several otolaryngologists who routinely treat chronic cough and, within the past year, a single provider performed superior laryngeal nerve blocks on 29 patients, with the majority of the injections occurring within the last 2-3 months. Therefore, we are confident in our ability to recruit 50 patients within 1 year. Assuming a dichotomous outcome of >50% improvement or not, a 70% treatment effect, a 25% possible incidence of improvement in placebo, and an 80% confidence level, we would need 18 patients in each group (total N=36) to power our study.

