**Figure 3. Anatomic Target of Superior Laryngeal Nerve Blocks.**

During the procedure, the thyroid cartilage, hyoid, and thyrohyoid membrane are palpated as key anatomic landmarks. The target of the injection, the superior laryngeal nerve, pierces the thyrohyoid membrane superior to the superior laryngeal artery. The plunger is drawn back prior to injection to ensure needle tip is not intravascular. Illustration by author.

Patients will be provided a log to track their progress throughout treatment. This will include a visual analogue scale to be completed daily after each injection to document cough severity, as well as opportunities to document any adverse effects or general comments. An example of this log can be seen in Figure 4. At each follow up visit, patients will provide a dichotomous answer (Yes or No) if they experienced improvement in cough and will disclose how long the improvement lasted. They will also fill out the Leicester Cough Questionnaire (LCQ), a validated 19-question quality of life survey for chronic cough. The LCQ will be the study's primary outcome measure. Please see Appendix 1 for a copy of the Leicester Cough Questionnaire. After the last injection, patients will return to the clinic in three months or opt to be contacted via telephone to assess if symptoms have returned.

Date of last injection: _____
 
WEEK 1  Please mark on the line below with a "X" how severe you believe your cough is. The far left indicates no cough at all, and the far right is indicative of the most severe cough.
 
Day 1 no cough ..... severe cough
 
Day 2 no cough ..... severe cough
 
Day 3 no cough ..... severe cough
 
Day 4 no cough ..... severe cough
 
Day 5 no cough ..... severe cough
 
Day 6 no cough ..... severe cough
 
Day 7 no cough ..... severe cough
	

Date of last injection: _____
 
WEEK 2  Please mark on the line below with a "X" how severe you believe your cough is. The far left indicates no cough at all, and the far right is indicative of the most severe cough.
 
Day 1 no cough ..... severe cough
 
Day 2 no cough ..... severe cough
 
Day 3 no cough ..... severe cough
 
Day 4 no cough ..... severe cough
 
Day 5 no cough ..... severe cough
 
Day 6 no cough ..... severe cough
 
Day 7 no cough ..... severe cough
	

Any side effects?
	
Any side effects?

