## 15.0 Risks to Subjects

While no major adverse effects following SLN blocks for chronic cough have been reported in the current literature or found in our own experience, potential adverse events could include bruising, bleeding, laryngospasm, dysphagia and/or aspiration, swelling or fluctuance, dysphonia, or infection. Minor discomfort and self-limited globus sensation are not unexpected but typically mild. There is a theoretical potentially severe adverse event of intra-arterial injection resulting in blindness or stroke. The physician will always draw back on the syringe prior to injection to ensure that the needle is not intravascular and will perform a slow injection to prevent retrograde flow into the external carotid system to prevent this theoretical event. The study will be monitored by our Institutional Review Board and will be terminated early if any serious adverse reactions were to occur.

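### Section 13.0 ends the trial on any serious adverse event with no relatedness condition, so one event unrelated to the injection would stop it

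*Combined protocol and SAP*

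**What the plan says.** Section 13.0 gives the stopping rule as "If any serious adverse events were to occur, these would be immediately reported to the IRB and the study would terminate", and adds patient safety as the reason. It sets no condition on relatedness, expectedness or treatment arm. It names the primary investigator as the person who reviews the data.

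Section 15.0 states the rule again in different words: "The study will be monitored by our Institutional Review Board and will be terminated early if any serious adverse reactions were to occur".

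The protocol defines neither *event* nor *reaction*, describes no causality assessment, and gives no route for restarting after a stop.

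Three other places bear on the consequences:

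- Section 6.0 plans 50 patients, says that "we would need 18 patients in each group (total N=36) to power our study", and expects to enrol within a year.
- Section 10.0 has two injections two to three weeks apart, and says that "2 weeks after the second injection, participants will be unblinded". Placebo patients may then have two more injections, open-label, within the study.
- Section 10.0 also has a contact after the last injection, when "patients will return to the clinic in three months or opt to be contacted via telephone to assess if symptoms have returned".

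**The concern.** A serious adverse event can have any cause. Section 5.0 says that neurogenic cough mainly affects older adults, and the site's own series in Section 2.0 averaged 63.6 years of age. A fracture or a cardiac admission in such patients, including one in the saline arm, would meet the Section 13.0 trigger.

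Stopping after a possibly related event protects the remaining participants. Stopping after an unrelated one protects nobody from the injection, and it could leave the trial short of the 36 patients that it says it needs. The investigator would then have to end the study or depart from the protocol, because the text offers no third course.

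**Working it through.** **The wording.** The Section 13.0 trigger is any serious adverse event. The safety reason attached to it explains the rule but does not narrow it. The Section 15.0 trigger is any serious adverse reaction, a term that ordinarily implies a link to the treatment. No other section settles which is meant, so whoever applies Section 13.0 on its own terms must stop for an unrelated event.

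**The plan's own sample size.** Read 70% and 25% as the two response rates and the stated 80% as power, and assume a two-sided 5% test (the plan gives no alpha). The pooled formula gives

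n = [1.96·√(2·0.475·0.525) + 0.842·√(0.70·0.30 + 0.25·0.75)]² / 0.45² = (1.384 + 0.531)² / 0.2025 = 18.1 per group.

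This rounds up to 19 and agrees with the stated 18 to within rounding. By the same approximation, power at 18 per group is 79.8%. The margin above the stated requirement is 50 − 36 = 14 patients.

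**Assumed inputs.** The documents give no all-cause serious-event rate. I take a per-patient risk p of 0.1%, 0.5%, 1% or 2% over 15 weeks (about 2 weeks between injections plus about 13 weeks to the three-month contact). The weekly hazard is h = −ln(1 − p)/15. The blinded period is taken as 5 weeks (up to 3 weeks between injections plus 2 weeks to unblinding).

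**Chance of at least one event in 50 patients.**
- 15 weeks: 1 − (1 − p)^50. For p = 1%: 1 − 0.99^50 = 0.39499.
- 5 weeks: 1 − exp(−50·5·h). For p = 1%: h = 0.000670, so 1 − exp(−0.1675) = 0.154.

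**Chance that fewer than 36 finish the blinded 5 weeks.** Section 6.0 says "we are confident in our ability to recruit 50 patients within 1 year". With even entry, patients arrive every 52/50 = 1.04 weeks. Add up the patient-weeks at risk until the 36th patient has completed 5 weeks:
- 5-week exposure: 36·5 + (3.96 + 2.92 + 1.88 + 0.84) = 189.6.
- 15-week exposure: 26·15 + (10·5 + 1.04·45) + 9.6 = 390 + 96.8 + 9.6 = 496.4.

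The chance of a stop before then is 1 − exp(−h × patient-weeks).

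| Assumed p over 15 weeks | Per 100 person-years | Any event in 50, 15 weeks | Any event in 50, 5 weeks | Fewer than 36 finish, 15 weeks | Fewer than 36 finish, 5 weeks |
|---|---|---|---|---|---|
| 0.1% | 0.35 | 5% | 2% | 3% | 1% |
| 0.5% | 1.74 | 22% | 8% | 15% | 6% |
| 1% | 3.48 | 39% | 15% | 28% | 12% |
| 2% | 7.00 | 64% | 29% | 49% | 23% |

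**Power, as a secondary check.** This covers only the dichotomous outcome, 70% versus 25%, by exact enumeration of the uncorrected chi-squared test at two-sided 5%. Power is 93% with 25 per arm. In a simulation of 40,000 trials per case, stopping at the first event, average power at p = 0.5%, 1% and 2% is 90%, 87% and 81% with 5-week exposure, and 86%, 79% and 69% with 15-week exposure.

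**Can the cited series fix the rate?** For the series of 18, Section 2.0 says "No significant adverse outcomes were reported". It reports no adverse effects in the series of 10, and for the site's 23 it says "There were no major adverse events". Treated as 0 of 51, the one-sided 95% upper limit is 1 − 0.05^(1/51) = 5.7%. These series describe effects of the injection, so they do not give a rate of unrelated events.

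**The case against.** The best reply is that the literal reading is the less likely one. The protocol uses its safety terms loosely. Every adverse event that Section 15.0 names is an injection complication, and much of Section 13.0 is about side effects of, and concerns with, the injections. Read together, the two sections can state one rule: stop for a serious injection complication. This stands as far as intent goes, and a reader who inferred that the two sections contradict each other would go beyond the text. It does not remove the problem, because Section 13.0 still says *any* and nothing else limits it.

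A second reply is that stopping at the first serious event is a defensible caution. Section 15.0 names stroke and blindness as theoretical risks, and the cited experience is 51 patients. That stands for events that may be related, and the stop for them should stay.

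A third reply concerns size. A reader might infer from the larger percentages that the trial is likely to be cut short or underpowered. The documents do not support this. No rate is given, and at 0.1% the effect is negligible. On the blinded period, average power for the dichotomous outcome is still 81% at the highest rate assumed, although an average hides the individual trials that stop early. The 15-week figures also require events to be picked up through a contact meant to assess symptom return. Equally, 15 weeks should not be read as an upper bound, because the open-label injections offered to placebo patients add time at risk that the calculation leaves out.

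Last, a relatedness judgement has its own weakness. Section 10.0 leaves the injecting practitioner unblinded, and a saline-arm event may be called unrelated more readily. This stands, and it is why the IRB has to agree before the study resumes.

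**Conclusion.** The point holds as a defect in a stated rule. As written, Section 13.0 would end the trial for a single serious event unrelated to the injection, in either arm, with no gain in safety. Section 15.0 suggests a narrower intent that Section 13.0 does not express.

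The size cannot be settled from the documents. The results in the table run from negligible to large, and nothing in the documents selects a value. They rest on the assumed rates, a constant hazard, even recruitment over one year and independence between patients. The Leicester Cough Questionnaire is the primary outcome and no standard deviation is given for it, so no loss is computed there and none should be inferred from the dichotomous figures. The case for changing the text rests on the wording and the low cost of correcting it, and does not depend on any one of these probabilities.

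**What to change.** Use one trigger, in identical words, in Sections 13.0 and 15.0:

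> Every serious adverse event is reported to the IRB immediately and injections pause until the IRB has reviewed it. The study terminates if the event is judged at least possibly related to the injection by the investigator or the IRB; it resumes only if the IRB agrees the event is unrelated.

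This keeps the stop for any possibly related event and immediate reporting of every serious event. It uses the IRB, which Section 15.0 already names as monitoring the study. The cost is a wording amendment in two sections, with no new staff and no change to sample size or analysis.

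There are two downsides. A relatedness judgement, made first by an investigator who is not blinded, replaces an automatic stop; the pause and the need for IRB agreement limit this. A long pause could also carry patients past the 1–4 week follow-up window in Section 10.0, outside which their data are removed, so follow-up assessments should go ahead on schedule while injections are on hold.
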